### **Sample size and analytical plan:**

#### Sample Size Calculation:

Lindell et al (2018), who evaluated the impact of a psychiatric clinical pharmacists intervention on the change in PHQ-9 and/or GAD questionnaire scores (14), reported a baseline PHQ-9 mean of 15.2 (Standard deviation [SD] of 6.9) and GAD mean of 12.0 (Standard deviation [SD] of 5.8).

Using those reported values and the following assumptions of an 80% power and a 2 sided alpha of 0.05, a sample size of:

- 84 patients (42 in each group) is required to detect a 4.3 point difference in the mean reduction in PHQ-9 scores between the intervention and control group
- 80 patients (40 in each group) are required to detect a 8.3 point difference in the mean reduction in GAD scores between the intervention and control group.

We selected the larger sample size of 84 patients and inflated it by 10%(47 in each group) to account for potential losses to follow-up and withdrawal of consent.

A Data Safety monitoring board will be formed to review adverse events, and data will be sent once recruitment reaches 25% (24 participant) recruitment.

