## **Outcomes:**

### **Primary outcomes:**

The primary outcome is the mean score difference in PHQ-9 and GAD-7 scores from baseline to end of study participation, between the intervention and standard pharmacist care groups.

- Both PHQ-9 and GAD-7 are validated tools for measuring major depressive disorder and generalised anxiety, respectively, in the primary care setting. They are brief and can be self-administered, with similar results yielded with health care provider administered reports. These are desirable given the time restraints and competing demands we anticipate for community pharmacist partners participating in the study(11, 12).
- PHQ-9 scores reflect depression severity; Ranges from 0-27 (Scores: 0-4 none/minimal, 5-9 mild, 10-14 moderate, 15-19 moderately severe, 20-27 severe) (13).
- GAD-7 scores reflect anxiety severity; Ranges from 0-21 (Scores: 0-4 none/minimal, 5-9 mild, 10-14 moderate, 15-21 severe) (13)

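### The 80% power for a 4.3-point difference in mean PHQ-9 reduction rests on the SD of baseline scores; the analysis as written does not secure it unless the baseline to month 6 correlation is about 0.44 or more

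*Protocol*

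**What the plan says.** The Sample Size Calculation gives one PHQ-9 variability figure and labels it as baseline: the cited pilot "reported a baseline PHQ-9 mean of 15.2 (Standard deviation [SD] of 6.9) and GAD mean of 12.0 (Standard deviation [SD] of 5.8". It proceeds "Using those reported values and the following assumptions of an 80% power and a 2 sided alpha of 0.05" and concludes that "84 patients (42 in each group) is required to detect a 4.3 point difference in the mean reduction in PHQ-9 scores". The total is then "inflated it by 10%(47 in each group", which makes 94.

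Under Primary outcomes, the tested quantity is again a change: "The primary outcome is the mean score difference in PHQ-9 and GAD-7 scores from baseline to end of study participation".

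The Analytical Plan names ANCOVA for the primary outcome. Its covariates are those that differ between the groups at p below 0.25. The baseline score is not named as a covariate that is always included.

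The protocol gives no SD of change, no month 6 SD and no correlation between baseline and month 6 scores.

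**The concern.** The SD of scores at one visit and the SD of each patient's change between two visits are different quantities, linked by the correlation between the visits. The protocol supplies the first and attaches its power claim to the second. With a low correlation, change is more variable than the baseline score and power falls below the stated figure; with a high correlation, power exceeds it.

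At stake is how the result will be read. If the true effect were 4.3 points and the correlation low, the trial would miss it more often than the 20% implied, and a non-significant result could be over-read as evidence against an effect of that size.

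**Working it through.** **Inputs from the protocol.** SD 6.9 (baseline PHQ-9), difference 4.3, 42 per group, two-sided alpha 0.05 (Sample Size Calculation).

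**Assumptions, because the protocol gives no figures.** Month 6 SD equal to 6.9 (varied in step 5), correlation r from 0.2 to 0.7, 42 completers per group, normally distributed scores.

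**1. Reproduce the stated figure.** The noncentrality of the two-sample t-test is 4.3 / (6.9 × sqrt(2/42)) = 4.3 / 1.506 = 2.86 on 82 degrees of freedom, giving power 80.6%. With 41 per group it is 79.6%. So 42 is exactly the t-test answer when 6.9 is used as the SD of the reduction. The dropout step also reproduces: 84 / 0.9 = 93.3, hence 94, or 47 per group.

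**2. Unadjusted change score.** SD of change = 6.9 × sqrt(2(1 − r)). At r = 0.3 this is 6.9 × sqrt(1.4) = 8.16. It equals 6.9 when r = 0.5.

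**3. ANCOVA with the baseline score always included.** Residual SD = 6.9 × sqrt(1 − r²). At r = 0.3 this is 6.9 × sqrt(0.91) = 6.58. It never exceeds 6.9.

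**4. The rule as written.** In simulated trials the baseline score entered the model only when its between-group p-value was below 0.25; otherwise change was compared unadjusted. The baseline score was the only candidate covariate. Under randomisation it entered in about 25% of trials.

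| r | SD of change | Power, unadjusted change | Difference detectable with 80% power, unadjusted | Power, p < 0.25 rule (simulated) | Power, baseline always adjusted |
|---|---|---|---|---|---|
| 0.2 | 8.73 | 61% | 5.4 | 67% | 82% |
| 0.3 | 8.16 | 67% | 5.05 | 72% | 84% |
| 0.4 | 7.56 | 73% | 4.7 | 78% | 87% |
| 0.5 | 6.90 | 81% | 4.3 | 84% | 90% |
| 0.6 | 6.17 | 88% | 3.8 | 91% | 94% |
| 0.7 | 5.34 | 95% | 3.3 | 96% | 98% |

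Power crosses 80% at r of about 0.49 for unadjusted change and about 0.44 under the rule as written. With the baseline score always in the model, power is about 80% at r = 0 and rises from there.

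**5. Unequal SDs.** With month 6 SD s, the SD of change is sqrt(6.9² + s² − 2r × 6.9 × s), which equals 6.9 when r = s / (2 × 6.9). The threshold is 0.36 for s = 5, 0.43 for s = 6 and 0.58 for s = 8. A larger month 6 SD also affects the adjusted analysis: at s = 8 and r = 0.3 the residual SD is 8 × sqrt(0.91) = 7.63 and power is about 72% by t-test (73% by normal approximation).

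**The case against.** The strongest reply is that the protocol plans ANCOVA, not a t-test on change. If the baseline score is in that model and the month 6 SD is no larger than 6.9, then 6.9 is conservative and the stated power is met at any correlation. Using a single-visit SD to size an ANCOVA is a common and safe choice. This is correct, and it is why the remedy needs no more patients. It does not rescue the text as it stands, because the p < 0.25 rule leaves the baseline score out in about three trials in four. A statistical analysis plan, which is not shown, might add the score as a fixed covariate, but the protocol's own rule says otherwise.

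It is also fair to say that the harm depends on an unknown. Nothing in the protocol shows that the correlation is low; that is an assumption.

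Three stronger readings are tempting, and the document does not support them:

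- A reader might infer that the 80% holds only at a correlation near 0.5. That value is a floor for the unadjusted analysis; above it, power exceeds 80%.
- A reader might infer that the trial is underpowered. The correlation and month 6 SD are not given, so power may lie on either side of 80%.
- A reader might infer that the GAD-7 line has the same fault. It does not: 8.3 points with SD 5.8 needs about 9 per group, not 40, and 40 per group detects about 3.7 points. Even at r = 0, 40 per group gives 99% power for 8.3 points. That line does not reproduce from its own inputs, which is a separate error.

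**Conclusion.** The point holds as a mismatch between the input and the claim. The 80% was obtained by entering the SD of baseline PHQ-9 scores as the SD of the reduction, and the covariate rule does not guarantee the adjustment that would make this safe.

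With equal SDs and 42 completers per group, power under the plan as written runs from about 67% at r = 0.2 to 96% at r = 0.7. It falls short of 80% for r under about 0.44 (about 0.5 if change is never adjusted). These thresholds move with the month 6 SD. The finding does not show that N is too small: with the baseline score always adjusted for, the same 84 patients give 82% at r = 0.2 and 90% at r = 0.5. The correction is worth making because it is nearly free and gives the stated power a defined basis.

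**What to change.** Two changes are needed together, since either alone would leave the sizing and the analysis out of step.

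1. In the Analytical Plan, name the baseline score of the same scale as a fixed covariate in the primary ANCOVA, whatever its between-group p-value.
2. In the Sample Size Calculation, replace the PHQ-9 statement with: *42 per group give at least 80% power for a 4.3-point baseline-adjusted difference, assuming a month 6 SD no larger than 6.9.*

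If an unadjusted change score is kept instead, state the assumed correlation and the resulting SD of change, and give power as a range (61% to 95% for r = 0.2 to 0.7 with equal SDs).

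The cost is two wording changes and a stated power that is openly conditional on the month 6 SD. The baseline score is already collected, and N stays at 94. The GAD-7 line needs its own correction, because these changes do not repair its arithmetic.

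### The GAD-7 sample-size line does not reproduce: 8.3 points with SD 5.8 needs about 9 patients per group, while the stated 40 per group corresponds to about 3.7 points

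*Protocol*

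**What the plan says.** The Sample Size Calculation section of the protocol takes its inputs from a published pilot of clinical pharmacist services: a "baseline PHQ-9 mean of 15.2 (Standard deviation [SD] of 6.9" and a "GAD mean of 12.0 (Standard deviation [SD] of 5.8". It adds "assumptions of an 80% power" and "a 2 sided alpha of 0.05". Two results follow:

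- PHQ-9: "84 patients (42 in each group) is required to detect a 4.3 point difference in the mean reduction in PHQ-9 scores".
- GAD-7: "80 patients (40 in each group) are required to detect a 8.3 point difference in the mean reduction in GAD scores".

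The larger figure, 84, is adopted and raised by 10% to 47 per group. The section gives no other SD, no correlation between baseline and follow-up, and no adjustment of alpha for having two measures.

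The Primary outcomes section makes the between-group difference in change on both scales the primary outcome. It describes the anxiety scale as follows: "GAD-7 scores reflect anxiety severity; Ranges from 0-21".

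**The concern.** The two lines share power, alpha and allocation, and they differ only in SD and target difference. The GAD-7 line has a target almost twice as large (8.3 against 4.3) and a smaller SD (5.8 against 6.9), yet it asks for nearly as many patients (80 against 84). Required numbers scale with the square of SD over difference, so that cannot be right.

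The target is also implausible in itself. A between-group difference of 8.3 is 69% of the assumed baseline mean (8.3/12.0). It is wider than any severity band that the protocol lists for GAD-7; the mild and moderate bands each span five points.

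At stake is the stated design target for one of the two scales in the primary outcome. An ethics board, journal or reader who takes 8.3 as that target would regard a true 4-point benefit as less than half of it. On the protocol's own inputs, 4 points exceeds what 40 per group can detect with 80% power.

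**Working it through.** **Inputs**, all from the Sample Size Calculation section: two-sided alpha 0.05; power 80%; equal groups; SD 6.9 and difference 4.3 for PHQ-9; SD 5.8 and difference 8.3 for GAD-7.

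**Formula.** The normal approximation for two means is n per group = 2 × (1.960 + 0.842)² × SD² / difference² = 15.70 × (SD/difference)². The exact t-test calculation (noncentral t) adds about one patient per group.

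**Step 1: reproduce the PHQ-9 line.** 15.70 × (6.9/4.3)² = 40.4. The t-test gives 41.4, rounded up to 42 per group. This is the stated figure, so the method is a two-sample t-test with the baseline SD used as the SD of the reduction.

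**Step 2: apply the same method to the GAD-7 line.** 15.70 × (5.8/8.3)² = 7.7. The t-test gives 8.74, rounded up to 9 per group, or 18 in total. The protocol says 40 per group, 80 in total. Power for 8.3 points with 40 per group is above 99.99%.

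**Step 3: look for a setting that gives 40.**

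| Setting, difference 8.3 | n per group |
|---|---|
| One- or two-sided, alpha 0.05 or 0.025, power 80%, 90% or 95%, SD 5.8 (normal approximation) | 7 to 15 |
| PHQ-9 SD of 6.9 used by mistake (normal approximation) | 11 |
| SD of a change score with zero correlation, 5.8 × √2 (normal approximation; t-test) | 16; 17 |

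The last setting would also move the PHQ-9 line to 81 per group and so break the line that works. For 8.3 points to need 40 per group, the SD would have to be about 13.1, more than twice the stated 5.8.

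**Step 4: work back from 40 per group.** With SD 5.8 and 80% power, the t-test detects 3.68 points (3.63 by the normal approximation).

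**Step 5: test a likely source of the slip.** 12.0 − 8.3 = 3.7. For 3.7 points, 15.70 × (5.8/3.7)² = 38.6. The t-test gives 39.56, rounded up to 40 per group, which is the stated figure. Power for 3.7 points is 80.4% at 40 per group and 82.4% at 42 per group. The ratio of the printed to the implied target is 8.3/3.7 = 2.2.

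**Step 6: effect on enrolment.** PHQ-9 sets the size: 42/0.90 = 46.7, rounded up to 47 per group, 94 in total. No GAD-7 figure enters this.

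**The case against.** The strongest case against is about weight, not arithmetic. The protocol gives two candidate sizes and adopts the PHQ-9 one, which is correct. The GAD-7 line therefore sets no design quantity: enrolment, outcome definitions and analysis stay as they are whichever figure is corrected. Nothing in the protocol uses 8.3 as a success threshold, and response and remission are defined separately, by a 50% reduction and a score below 5. All of this is true, and it means that the trial is not underpowered by this error. It does not make the statement harmless, because it gives a wrong target for a scale in the primary outcome.

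A second objection is that the arithmetic shows only that difference, SD and number are incompatible, not which one is wrong. Strictly, that stands. The match at 3.7 is strong circumstantial evidence, but the pilot's follow-up data are not in the protocol, so 3.7 must be confirmed against the source.

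A third is that the 82% power figure borrows assumptions. It takes the baseline SD as the SD of the reduction, and it applies one SD to a population admitted with MDD, GAD or both. This stands as a caveat. The SD is the protocol's own, and the Both Groups section has every participant complete both scales at months 0 and 6, so counting 42 per group for GAD-7 is defensible. Any power statement should name the SD assumption.

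**Conclusion.** The GAD-7 line is wrong as printed. With SD 5.8, 80% power and two-sided alpha 0.05, a difference of 8.3 needs 9 per group, and 40 per group corresponds to a difference of about 3.7. The stated target is too large by a factor of 2.2 or, if 8.3 is intended, the stated number is too large by a factor of more than four (40 against 9). The first reading is much the likelier, because 12.0 − 8.3 = 3.7 reproduces 40 per group exactly.

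That the three figures conflict rests only on what the protocol states, with the method confirmed by the PHQ-9 line. That 3.7 is the intended figure is an inference. The 82% power at 42 per group assumes that the SD of the GAD-7 reduction is 5.8 and that all 42 contribute scores. The error must be corrected, since it misstates the target for a component of the primary outcome, but it does not change the size of the trial.

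**What to change.** Check the GAD-7 figures against the cited pilot, then make one of two corrections in the Sample Size Calculation section:

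- If 8.3 was a follow-up mean, change the difference to 3.7 points and keep 40 per group. Add that the adopted 42 evaluable patients per group give about 82% power for 3.7 points on GAD-7, assuming that the reduction has SD 5.8 and that every evaluable patient has GAD-7 scores.
- If 8.3 is really the intended difference, change the required number to 9 per group (18 in total) and justify so large a target.

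The cost is one corrected figure and one added sentence. The total of 94, conduct and analysis are unchanged.

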#### **Analytical Plan:**

All analyses will be conducted on an intention to treat basis. In the case of missing data, a last observation carried forward approach will be used.

Primary outcome will be analysed using ANCOVA, adjusting for all covariates with  $p < 0.25$  between groups

Secondary outcomes will be analysed using ANCOVA, t-test or chi-square test where appropriate, adjusting for all covariates with  $p < 0.25$  between groups.

Trial and Data Management will be done by EPICORE Centre

---

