**Intervention Group (Pharmacist Interventions):**

Participants enrolled in the intervention group will receive pharmacist interventions, in addition to standard care outlined in the Alberta College of Pharmacist Standards of Practice for Pharmacist and Pharmacy technicians (9).

Unique pharmacist interventions will include the following (in person) at enrolment (month 0) and at the scheduled month 1, 3, and 6 in-person or telehealth pharmacist meetings:

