**Control Group (Standard Pharmacist Care):**

Patients randomised to the standard pharmacist care groups will receive:

- Standard pharmacist care, as outlined in the Alberta College of Pharmacist Standards of Practice for Pharmacist and Pharmacy technicians (9), and physician care with no specific interventions for the duration of the 6 month study period.
- Should participants from the usual care group drop out or the participant completes the 6 month study period, they will be offered care similar to the interventional group or standard pharmacist care but no data will be collected since their dropout or following study completion.

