**Both Groups**

- Indication of medication (i.e. MDD, GAD, or both) will be recorded by the pharmacist partner in the secured study electronic website/database.
- The electronic PHQ-9/GAD-7 questionnaire (Appendix 4) will be sent securely to and completed by the participant at enrollment (month 0) and prior to the participant's in-person scheduled month 6 (final). The questionnaire results will be available to the study investigator and pharmacist participants but linked only to the participant's study ID.
- Participants will receive a pamphlet copy of Alberta Health Services Access Mental Health resource pamphlet "Know Your Addiction and Mental Health Options" which provides information regarding walk-in services, crisis support, and urgent care (10). An equivalent alternative pamphlet can be developed and provided by the study team if this document becomes obsolete or additional update/information is required.

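### Last observation carried forward works on unequal schedules: a control dropout has only the baseline score, while an intervention dropout may carry a month-1 or month-3 score

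*Protocol*

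**What the plan says.** The protocol's Analytical Plan fixes both the analysis set and the missing-data rule: "All analyses will be conducted on an intention to treat basis", and "In the case of missing data, a last observation carried forward approach will be used". It does not say which observations may be carried forward. The primary model is ANCOVA.

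The measurement schedule differs by arm:

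- **Both arms.** Under Both Groups, the electronic questionnaire is "completed by the participant at enrollment (month 0) and prior to" the final month-6 visit. No other time point is given for control.
- **Intervention arm only.** The section Intervention Group lists its components as delivered "at enrolment (month 0) and at the scheduled month 1, 3, and 6 in-person or telehealth pharmacist meetings". The first component, Patient Assessment, is the recording of PHQ-9/GAD-7 scores.

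Data collection stops at dropout. For controls who leave or finish, "they will be offered care similar to the interventional group or standard pharmacist care but no data will be collected since their dropout". The Intervention Group section and the Continuity of care plan also end data collection at dropout.

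The primary outcome is the between-group difference in change "from baseline to end of study participation".

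**The concern.** One imputation sentence acts as two different rules. A control who drops out has a single score, the baseline, so the imputed change is exactly zero. An intervention participant who drops out after month 1 or month 3 has a score taken on treatment, and that score is carried to month 6. An intervention participant lost before month 1 carries baseline, as a control does.

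Everyone enrolled is starting medication, so some average improvement in both arms is a reasonable assumption. The rule then withholds that improvement from control dropouts and credits part of it to intervention dropouts. Because the analysis is by intention to treat, these imputed scores enter the primary comparison. With no true effect, this shifts the estimate towards the intervention and raises the false-positive rate. The 50% response outcome is affected too, because a carried baseline is a zero reduction and cannot count as a response.

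**Working it through.** **1. Inputs from the protocol (Sample Size Calculation).** PHQ-9 baseline mean 15.2, SD 6.9; target difference 4.3 points; two-sided alpha 0.05; power 80%; 42 per group, raised to 47 for 10% loss. The 10% is the only loss rate the protocol gives.

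**2. The plan's own figure.** Normal approximation: n = 2 × (1.960 + 0.842)² × 6.9² / 4.3² = 40.4, so 41 per group. The two-sample t-test gives 41.4, so 42 per group, or 84. Then 42 / 0.90 = 46.7, so 47. The stated PHQ-9 size reproduces.

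**3. Bias formula.** Let d be the share without a month-6 score (equal in both arms), X the mean month-6 improvement (equal in both arms, so no true effect), and C the mean improvement in the score carried forward by intervention dropouts.

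- Control mean change after imputation: (1 − d)X + d × 0
- Intervention mean change after imputation: (1 − d)X + dC
- Difference: **d × C** in favour of the intervention

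**4. Assumed values (the protocol gives none).** Improvement at months 1/3/6 of 2.5/4/5 points or 3.5/6/7 points. Dropout is either spread evenly over the three intervals, so that 0, the month-1 or the month-3 improvement is carried, or falls entirely after month 3.

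- Spread, 5-point course: C = (0 + 2.5 + 4)/3 = 2.17
- Spread, 7-point course: C = (0 + 3.5 + 6)/3 = 3.17
- All after month 3: C = 4 or 6

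**5. Results.** Each cell gives d × C in PHQ-9 points, then the simulated type I error. Simulation: no true effect, 47 per arm, SD 6.9, correlation 0.5 between baseline and month 6, ANCOVA on baseline, 3,000 trials per setting.

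| Dropout pattern | Course | 10% loss | 20% loss | 30% loss |
|---|---|---|---|---|
| Spread | 5 points | 0.22; 5.4% | 0.43; 6.6% | 0.65; 8.1% |
| Spread | 7 points | 0.32; 6.0% | 0.63; 7.9% | 0.95; 11.9% |
| All after month 3 | 5 points | 0.40; 6.8% | 0.80; 9.9% | 1.20; 16.7% |
| All after month 3 | 7 points | 0.60; 7.9% | 1.20; 15.9% | 1.80; 30.0% |

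The simulated mean differences agree with d × C to within about 0.02 points. Against the 4.3-point target, the 10% column is 0.22/4.3 = 5% to 0.60/4.3 = 14%. If all dropout falls before month 1, C = 0 and there is no bias.

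**6. Is the unequal schedule the cause?** A separate simulation (improvement of 4 to 8 points, 70% of it present in the carried score) gave 0.28 to 0.57 points at 10% loss and 0.54 to 1.12 at 20%. When both arms carried a score from the same time point, the mean difference was between −0.04 and +0.03 and type I error was about 4 to 6%.

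**7. When the direction changes.** Let f be the share of the intervention arm's month-6 improvement present in the carried score.

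- *Unequal dropout, no true effect.* Bias = X × [d(control) − d(intervention) × (1 − f)]. For the spread 5-point course, f = 2.17/5 = 0.43. With 10% control and 20% intervention loss: 5 × (0.10 − 0.20 × 0.567) = −0.07, slightly against the intervention.
- *True effect of 4.3 points, equal 10% loss.* Bias = d × [Xc − (1 − f)Xi], where Xc and Xi are the month-6 improvements in control and intervention. With Xc = 5, Xi = 9.3, f = 0.43: 0.10 × (5 − 0.567 × 9.3) = −0.03, about zero. Over Xc = 3 to 7 and f = 0.3 to 0.9 it runs from −0.21 to +0.59.

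**The case against.** The strongest reply is that the outcome assessments are the shared ones at months 0 and 6. On that view the month-1 and month-3 scores belong to the intervention's clinical content and were never meant to enter the imputation. A SAP that is not shown could say so, and step 6 shows that the asymmetry would then vanish. This stands as a possible repair but not as a reading of the protocol. The rule refers to the last observation without restriction, and scores at months 1 and 3 are recorded. The sections on randomization and on recording interventions mention scores at pharmacist meetings without naming an arm, but schedule no extra control questionnaire.

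A second reply is that the effect is small at 10% loss, and that carrying scores forward also dilutes a true effect. Both parts are correct and limit the point.

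A reader might infer several stronger claims that the document does not support:

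- *The rule always favours the intervention.* Step 7 shows otherwise.
- *Offering intervention-type care to those who leave draws controls out of the trial.* The same offer is made on completion, and nothing in the protocol shows that it would cause dropout.
- *A missing control always counts as a failure.* This holds for the 50% response outcome but not for remission. Inclusion sets no minimum score, so a carried baseline below 5 would count as remitted.
- *The phrase on end of participation builds in the asymmetry.* Both Groups calls month 6 final, and other sections refer to a six-month period. The phrase is loose and needs only clarifying.

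**Conclusion.** The point holds with conditions. As written, the rule imputes the two randomised arms differently. With average improvement, similar dropout and no true effect, it produces a false PHQ-9 benefit of about 0.2 to 0.6 points at the planned 10% loss, with type I error of about 5 to 8%. At an assumed 20% loss these become about 0.4 to 1.2 points and 7 to 16%.

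The top of the 30% column in the working combines three assumptions absent from the protocol (30% loss, all of it after month 3, and a 7-point improvement) and should not be quoted as the expected error rate. The formula applies equally to GAD-7, but no GAD-7 figures were computed.

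Severity is moderate at the planned 10% loss and serious if loss reaches 20% or more.

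**What to change.** 1. State month 6 as the primary time point in Primary outcomes.
2. Amend the Intervention Group, Control Group and Continuity of care sections so that the month-6 electronic PHQ-9/GAD-7 goes to every randomised participant who has not withdrawn consent to data collection. The care offered after dropout need not change.
3. Replace last observation carried forward as the primary method. Use a likelihood-based analysis, or multiple imputation followed by the baseline-adjusted ANCOVA, with a control-based or delta-shift sensitivity analysis.
4. If any carry-forward is kept, restrict it to the shared month-0 and month-6 assessments in both arms.

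Item 2 matters most. With only a baseline score for control dropouts, no imputation model can add much about them, and month-6 scores that were never collected cannot be recovered at analysis.

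**Cost.** Protocol wording, possibly consent wording and ethics review, one further use of the existing electronic link, and slightly more analysis work. Month-6 scores from controls who took up intervention-type care after leaving may narrow the difference between arms; that is consistent with the stated intention-to-treat basis. Measuring controls at months 1 and 3 would also equalise the schedules, but score recording at those visits is listed as part of the intervention, so it would alter the comparison.

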**Recruitment:**

Potential participants will be identified and approached by the pharmacist partners (pharmacists with APA and PraCID) if they are picking up or dropping off their prescription for a medication listed in Appendix 1 and 2.

Medication indication will be verified with the patient for the treatment of diagnosed MDD and/or GAD (and if additional verification is required--collateral from physician, Netcare consult note, or pharmacy record).

As part of the standard of pharmacist practice (as outlined in the Alberta College of Pharmacist Standards of Practice for Pharmacist and Pharmacy technicians [9]), a patient is clinically assessed for pharmacotherapy appropriateness by the pharmacist partner. This process is performed by the pharmacist partner and is the initial screen to determine if the patient meets any inclusion or exclusion criteria.

Determined by the pharmacist partner, if a patient meets the inclusion criteria for the study and does not meet any exclusion criteria, the patient will be asked if he/she wants to participate in the study and be provided with a formal invite letter to review.

If the patient agrees on participating, he/she will be asked to sign a written informed consent form. After signing the consent form, the patient will be enrolled in the study and randomised as a study participant using the secured electronic study website/database (developed by EPICORE and secured at the University of Alberta research office).

The participant's physician will receive the notification letter for physicians, from the pharmacist partner, to inform him/her that the participant has agreed to participate in the study. Should the physician refuse to have the participant participate in the study, the participant will not be enrolled into the study.

Should the participant decline recruitment into the study, they will continue to receive the same level of pharmacist care as outlined in the Alberta college of pharmacists standards of practice (9).

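### The only missing-data rule, last observation carried forward, cannot supply a missing month 0 score, so some randomised participants cannot enter the change or 50% response analyses despite the intention-to-treat promise

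*Protocol*

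**What the plan says.** The Analytical Plan states "All analyses will be conducted on an intention to treat basis" and then "In the case of missing data, a last observation carried forward approach will be used". It names no other missing-data method and makes no exception for the first score.

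The primary outcome is "the mean score difference in PHQ-9 and GAD-7 scores from baseline to end of study participation", compared between arms. The first secondary outcome, response, is a fall of at least 50% from baseline on each scale. The two remission outcomes need only a score below 5.

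On timing, the Recruitment section says "After signing the consent form, the patient will be enrolled in the study and randomised as a study participant". Under Randomization, the electronic link that delivers the questionnaire also carries the group allocation, so the form arrives after randomisation with the arm known.

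Under Both Groups, the questionnaire "will be sent securely to and completed by the participant at enrollment (month 0") and again before month 6. For the intervention arm, "Unique pharmacist interventions will include the following (in person) at enrolment (month 0"), and recording the questionnaire scores is among the tasks listed. The Control Group section lists standard care and no month 0 study meeting.

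**The concern.** Carrying forward needs an earlier value, and month 0 has none. A participant who leaves the first form blank but completes month 6 has been measured at the endpoint, yet has no change from baseline and no response status. The one rule the protocol gives cannot create either. Applied as written, it leaves a randomised, followed-up participant out of the primary analysis, which conflicts with the intention-to-treat statement that precedes it.

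Two things are at stake. The smaller is precision, since usable month 6 scores are lost. The larger is bias: if baselines are missing more often in one arm, and those participants differ in outcome, the groups compared are no longer quite the groups randomised.

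**Working it through.** **Can such participants exist?** Yes, by design.

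1. Randomisation follows consent (Recruitment; Randomization).
2. The questionnaire link contains the allocation, so the form follows randomisation.
3. No section makes a completed form a condition of randomisation.
4. The in-person alternative is for participants who cannot be sent a link, and it is tied to scheduled pharmacist meetings.

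**Which outcomes are affected?**

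| Outcome | Needs month 0? | Computable with month 6 only? |
|---|---|---|
| Change in PHQ-9 / GAD-7 (primary) | Yes | No |
| 50% response | Yes | No |
| Remission, score <5 | No | Yes |

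**The plan's own sample size.** Inputs from the Sample Size Calculation: difference 4.3, SD 6.9, two-sided alpha 0.05, power 80%. The two-sample t-test gives 41.4, so 42 per arm, as stated. Inflation: 42 / 0.9 = 46.7, so 47 per arm, also as stated. Power at 42 v 42 is 80.6% and at 47 v 47 is 84.8%.

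**Loss of power, on assumed rates.** The documents give no rate of missing baselines. Assume none missing in the intervention arm and 10% or 20% in controls, with no other losses:

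- 10%: 47 × 0.9 = 42.3, so 47 v 42; power 82.7%.
- 20%: 47 × 0.8 = 37.6, so 47 v 38; power 80.6%.

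If other losses have already used the 10% allowance (42 per arm), the same rates give 42 v 38 with power 78.5%, and 42 v 34 with power 76.0%.

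**Shift in the estimate, on assumed rates.** Let p be the share of controls omitted. The full control mean is (1 − p) × retained mean + p × omitted mean. Using the retained mean alone shifts it by p × (retained mean − omitted mean). With a further assumed gap of 2 to 4 points in mean change:

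- smallest: 0.10 × 2 = 0.2 points
- largest: 0.20 × 4 = 0.8 points

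against a target difference of 4.3.

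**Does the remedy help?** A simulation assumed a true effect of −4.3, SD 6.9, a month 0 to month 6 correlation of 0.5, and about 19% of control baselines missing. Missingness was made moderately dependent on one quantity at a time:

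| Missingness depends on | Change score, participants with a baseline | Month 6 ANCOVA, pooled-mean baseline |
|---|---|---|
| Baseline | −4.91 | −4.85 |
| Month 6 score | −3.74 | −4.57 |
| Change | −3.15 | −4.05 |

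The remedy is closer to −4.3 in each row but not free of bias: it is off by 0.55, 0.27 and 0.25, against 0.61, 0.56 and 1.15. Under random missingness the change-score analysis was unbiased. A similar simulation put the standard error at about 1.24 for the remedy and 1.48 for the change-score analysis.

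**The case against.** The strongest reply is that handling of a missing baseline is ordinary SAP material. The protocol nowhere says that carrying forward will be applied to month 0, or that participants without a baseline are excluded. Intention to treat is also undefined here and could mean only analysis as allocated. Part of this stands: exclusion is a consequence of the stated rule, not a stated intention, and a SAP that is not shown could add a provision. But the protocol is not silent. It fixes one rule for missing data in general, and that rule cannot deliver the primary outcome for these participants. Also, the timing of the form is a matter of conduct that a SAP cannot repair.

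A reader might infer that the losses would fall mostly on controls, because an intervention pharmacist would catch a blank form while a control's link goes unprompted. The documents do not support that. They give no rates by arm. The form is planned for both groups at enrolment, and controls also meet the pharmacist when they are recruited and sign consent. The intervention pharmacist is told to record scores from a completed tool, not to chase a missing one. What remains is a possible imbalance, because only one arm has a listed month 0 study contact.

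It is also fair to say that the affected group is narrow, and that assuming no missing baselines in the intervention arm is the choice least favourable to the plan.

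**Conclusion.** The defect holds as a conflict between the missing-data rule and the promised analysis set. Carrying forward cannot fill a first observation, and the protocol's sequence allows randomised participants to lack one. It touches the primary change outcome and 50% response on both scales, and leaves remission alone.

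The size is unknown. On the assumed rates it is modest: power of 83% to 81% instead of 85%, and a shift of about 0.2-0.8 points against 4.3. Power falls below 80% at these rates only if the dropout allowance is already spent. Bias matters more than power, and it depends on missingness being related to outcome and unequal by arm, neither of which the documents establish. Saying that the comparison is no longer between randomised groups would therefore go too far. The point merits correction because the remedy is cheap and the primary outcome is involved.

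**What to change.** 1. **Conduct.** Have the PHQ-9/GAD-7 completed before randomisation and before allocation is disclosed, and make completion a condition of randomising. This removes the cause in both arms. It means separating the month 0 form from the link that carries the allocation, and a short extra step at enrolment. It cannot help anyone already randomised.
2. **Analysis.** Use the month 6 PHQ-9 (and GAD-7) score as the ANCOVA outcome, with the month 0 score always a covariate, whatever the p < 0.25 screen shows. With baseline in the model, the treatment effect on the month 6 score is the same quantity as the effect on change.
3. **Missing month 0.** State that carrying forward does not apply. Set the covariate to the pooled mean of both arms, ignoring allocation, so that everyone with a month 6 score is analysed.
4. **Response.** Report by arm how many participants cannot be classified for 50% response. The covariate imputation does not rescue this outcome.

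Items 2 to 4 cost a few sentences in the Analytical Plan and need no added patients or data. The downside is that mean imputation of the covariate leaves some bias if missingness depends on baseline severity and differs by arm, which is why item 1 comes first.
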